**Table 5. Systemic Solicited Adverse Events**

Systemic (Subjective)	Mild (Grade 1)	Moderate (Grade 2)	Severe (Grade 3)
Fatigue/Malaise	No interference with activity	Some interference with activity	Incapacitating, prevents daily activity, may necessitate medical care or absenteeism
Headache	No interference with activity	Some interference with activity	Incapacitating, prevents daily activity, may necessitate medical care or absenteeism
Nausea	No interference with activity	Some interference with activity	Incapacitating, prevents daily activity, may necessitate medical care or absenteeism
Body ache/myalgia (not at injection site)	Less active than normal without interference with essential daily tasks (e.g. eating, sleeping)	Less active than normal with interference with essential daily tasks (e.g. eating, sleeping)	Incapacitating, prevents daily activity, may necessitate medical care or absenteeism
General activity level	Less active than normal without interference with essential daily tasks (e.g. eating, sleeping)	Less active than normal with interference with essential daily tasks (e.g. eating, sleeping)	Incapacitating, prevents daily activity, may necessitate medical care or absenteeism
Vomiting	1-2 times a day	3-4 times a day	>4 times a day
Systemic (Quantitative)	Mild (Grade 1)	Moderate (Grade 2)	Severe (Grade 3)
Fever (°C) – ORAL	≥38.0 - <38.3 ≥100.4 < 101° F	≥38.3 - <39 ≥ 101 - < 102° F	≥39 ≥ 102° F

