**b. Phase 2 Trial:** A multicenter, phase II, randomized, double-blind, stratified study enrolled individuals ≥65 years of age to receive either 15 µg versus 60 µg of TIV. Oral temperature, injection site, and systemic symptoms and signs were recorded in a diary daily for one week after immunization. Sera were obtained before immunization and one month after immunization. A total of 414 subjects were enrolled, 206 received HD-TIV and 208 received standard dose TIV (SD-TIV). Subjects given the HD-TIV reported more local and systemic reactions but only local pain and myalgia were significantly increased. The HD-TIV vaccine induced a higher frequency of serum antibody increases (≥4-fold) in both HAI (16.8-27.9%) and neutralization tests (11.9-24.5%) for all three vaccine viruses in the total group as well as in subjects vaccinated and not vaccinated the previous year. Mean titers of antibody attained, the magnitude of antibody increases, and the frequencies of persons with final HAI antibody titers ≥1:32, ≥1:64, and ≥1:128 were all greater for the HD-TIV group in both serologic tests (e.g., HAI and neutralization assays), for all titer groups ≥1:32, ≥1:64, and ≥1:128), and for all vaccine viral strains compared to the SD-TIV.

**c. Phase 3 and 3b Trials, HD-TIV has Increased Immunogenicity and Efficacy in the Elderly:** A phase III, multicenter, randomized, double-blind study enrolled individuals ≥65 years of age to compare HD-TIV to SD-TIV. HD-TIV was administered to 2575 subjects and SD-TIV was administered to 1262 subjects. Individuals who received HD-TIV had higher mean post-vaccination GMT (**Table 1**). The HD-TIV vaccine met superiority criteria for both influenza A

Table 1.	HD-TIV	SD-TIV	GMT ratio
H1N1	116	67	1.7
H3N2	609	333	1.8
B	69	52	1.3

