**b. Definition of Adverse Event:**

**Adverse Event:** The International Conference on Harmonization (ICH) guideline E6 defines an AE as any untoward medical occurrence in a patient or clinical investigation subject administered a pharmaceutical product regardless of its causal relationship to the study treatment. An AE can therefore be any unfavorable and unintended sign (including an abnormal laboratory finding), symptom, or disease temporally related to the use of medicinal (investigational) product. The occurrence of an AE may come to the attention of study personnel during study visits and interviews or by a vaccine recipient presenting for medical care.

AEs must be graded for severity and relationship to study product (see below). Severity can be assessed by a licensed clinician (i.e., physician, nurse, nurse practitioner, physician's assistant). Relationship to study product can only be assessed by a clinician licensed to make medical diagnoses (i.e. physician, nurse practitioner, physician's assistant) listed on the Form FDA 1572.

Adverse events characterized as intermittent require documentation of onset and duration of each episode. The start and stop date of each reported AE will be recorded on the data collection forms and eCRF.

**c. Severity of Event:** AEs will be assessed by the clinician using a protocol defined grading system. For events not included in the protocol defined grading system, the following guidelines will be used to quantify severity:

- **Grade 1 -Mild:** events require minimal or no treatment and do not interfere with the patient's daily activities.
- **Grade 2 -Moderate:** events result in a low level of inconvenience or concern with the therapeutic measures. Moderate events may cause some interference with functioning.
- **Grade 3 -Severe:** events interrupt a patient's usual daily activity and may require systemic drug therapy or other treatment. Severe events are usually incapacitating or life threatening (any adverse drug experience that places the patient or subject, in the view of the investigator, at immediate risk of death from the reaction as it occurred. It does not include a reaction that had it occurred in a more severe form, might have caused death).

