**e. Reactogenicity:**

Reactogenicity events are AEs that are known to occur with this type of vaccine. The following Toxicity Grading Scales will be used to grade local and systemic (both quantitative and subjective) reactions:

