- b. Immunogenicity analysis:** The probability of achieving a 4-fold (or greater) rise in post-vaccination HAI titers relative to baseline, as well as the probability of a HAI titer greater than 1:40, will be estimated using a binomial model, using the full analysis set. We will calculate the Bayesian posterior distribution of the probabilities under all 4 combinations of SD- and HD-TIV crossed with a single dose and two doses. From these probabilities, odds ratios will be calculated along with 95% credible intervals. These quantities will be modeled as a logit-linear function of several covariates, including CD4+/CD8+/CD19+, and IgG/IgM levels, absolute neutrophil and lymphocyte count (or their ratio), time from post-transplant to enrollment, type of preparative regimen, donor status, and stem cell source. We will use normal priors with standard deviation of 5 for all logit-linear coefficients and the baseline mean, which are not informative when transformed to the probability scale. Scale (standard deviation) parameters will be given long-tailed half-Cauchy priors, also in the interest of being uninformative. In addition, the distributions of geometric mean HAI titers for high and SD-QIV recipients will be estimated via log-normal models, and expressed as ratios in order to evaluate the evidence for higher GMT in the HD-TIV sample, after one and two vaccines. The scale parameters for priors under the log-normal model will be increased by an order of magnitude relative to the logit-linear models to ensure that they do not influence the posterior estimates. We will compare each group to document if they meet serological criteria by WHO biological standards for influenza vaccines (>40% for seroconversion, GMT >2.5-fold increase, and >70% with ≥1:40). Subjects with missing data will be excluded from the analysis, but the sensitivity of the results to missingness will be formally analyzed by comparing posterior estimates under the range of possible outcomes for the missing individuals.
- c. Safety analysis:** For the primary analysis of the safety data, the proportion of subjects in each group (using full analysis set) experiencing at least one solicited AE will be calculated along with 95% posterior credible intervals. The difference between the rates of solicited AEs between the

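### Table 5 gives body ache/myalgia the same grades as general activity level, so myalgia without reduced activity has no grade and its severity summary is not comparable with the other symptoms

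*Combined protocol and SAP*

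**What the plan says.** Section C.16.e introduces Tables 4 and 5 with "The following Toxicity Grading Scales will be used to grade local and systemic (both quantitative and subjective) reactions". In Table 5, Grade 1 for fatigue/malaise, headache and nausea reads "No interference with activity". Grade 1 for body ache/myalgia reads "Less active than normal without interference with essential daily tasks (e.g. eating, sleeping"), Grade 2 reads "Less active than normal with interference with essential daily tasks (e.g. eating, sleeping"), and Grade 3 reads "Incapacitating, prevents daily activity, may necessitate medical care or absenteeism". The general activity row directly below has the same text in all three columns.

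Section C.16.c has a fallback scale, introduced by "For events not included in the protocol defined grading system, the following guidelines will be used to quantify severity".

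Secondary objective iii (section C.2.b) covers both the frequency and the severity of solicited systemic events and lists body ache/myalgia among them. In section C.17.c the primary safety analysis is a composite: the proportion of subjects in each group "experiencing at least one solicited AE will be calculated", with the arms compared by a difference in proportions. Individual events and their severities are summarized descriptively.

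**The concern.** A symptom scale should have a place for the symptom at its mildest. Here a subject with body ache who carries on as normal fits no column, and a subject with body ache and reduced activity scores on two rows for one complaint. Mild therefore means something different for myalgia than for every other symptom graded by its effect on activity.

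The item matters for this comparison. Section B.3.b reports that in the elderly phase 2 trial of the high-dose vaccine "only local pain and myalgia were significantly increased", and section B.4.b reports more body ache with the high dose in pediatric organ transplant recipients. Hypothesis 2 expects similar safety profiles. If mild myalgia dropped out of the count, part of a real difference between arms could be hidden. Even if every case is counted, staff at four sites have no defined grade for such a case and may handle it differently.

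**Working it through.** **1. The rows side by side (Table 5)**

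| Item | Lowest grade requires | Symptom present, activity unchanged |
|---|---|---|
| Fatigue, headache, nausea | Symptom without interference | Grade 1 |
| Body ache/myalgia | Reduced activity | No grade |
| General activity level | Reduced activity | Not applicable (the item is activity itself) |

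Pain and tenderness in Table 4 are also Grade 1 when daily activity is unaffected, and so is the general Grade 1 guideline in C.16.c. Myalgia is the exception among the symptom rows.

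**2. Does another rule fill the gap?** Not clearly. The C.16.c fallback is for events outside the protocol's grading system, and myalgia is inside it. C.16.b requires AEs to be graded for severity, so staff must grade an event that has no grade.

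**3. Which outputs are touched?**
- Myalgia severity summary (C.2.b.iii, C.17.c): affected whatever the counting rule, because mild myalgia has no defined place in it.
- Myalgia frequency: affected only if a symptom needs a grade to be counted.
- Composite of any solicited event: loses only subjects whose sole solicited event is ungraded myalgia.
- Grade 3: the myalgia text is the same as for fatigue, headache and nausea, so Grade 3 counts and the Grade 3 halting rule in C.16.j do not change.

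**4. Size, if ungraded myalgia is not counted.** The plan states no figure on this point to reproduce. The documents give neither myalgia rates by arm nor the share *m* of myalgia cases with unchanged activity, so both are assumed. The 69 subjects per arm come from C.17.a.

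Recorded rate = true rate × (1 − *m*). With the same *m* in both arms, the difference shrinks by (1 − *m*) and the risk ratio is unchanged. Power is the two-sided 5% normal approximation, Φ[(d − 1.96·SE0)/SE1], where SE0 = √(2p̄(1−p̄)/69) and SE1 = √(Σp(1−p)/69). At *m* = 0: p̄ = 0.225, SE0 = 0.0711, SE1 = 0.0699, so Φ[(0.15 − 0.1393)/0.0699] = 56%.

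| *m* | High dose | Standard dose | Difference (points) | Risk ratio | Odds ratio | Power |
|---|---|---|---|---|---|---|
| 0 | 30.0% | 15.0% | 15.0 | 2.0 | 2.43 | 56% |
| 25% | 22.5% | 11.25% | 11.3 | 2.0 | 2.29 | 42% |
| 50% | 15.0% | 7.5% | 7.5 | 2.0 | 2.18 | 28% |
| 75% | 7.5% | 3.75% | 3.8 | 2.0 | 2.08 | 16% |

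Other assumed pairs with the same 15-point gap (25% against 10%, 35% against 20%) give the same differences. Across the three pairs, power runs from 50.5% to 64.3% at *m* = 0 and from 24.7% to 34.3% at *m* = 50%.

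**5. Unequal loss.** Starting again from 30% against 15%:
- Losing 70% of high-dose and 50% of standard-dose cases gives 9.0% − 7.5% = 1.5 points.
- Losing 20% and 80% gives 24.0% − 3.0% = 21.0 points, wider than the true 15.

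The direction is fixed only if the loss is similar in both arms.

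**6. Composite.** If a share *s* of the ungraded cases have no other solicited event, each arm's composite falls by p × *m* × *s*. With equal *m* and *s*, the difference falls by *m* × *s* × (difference in p). This is smaller than the effect on myalgia itself whenever *s* is below 1. Scoring one complaint on two rows cannot change an any-event count.

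**The case against.** The strongest reply is that grading is not counting. No section says an ungraded symptom is discarded. Subjects record general reactions every evening (C.14), C.16.d says doubtful observations should be reported, C.16.g captures systemic reactions on the case report form with severity assessed by a clinician, and C.17.c sets no minimum grade. This stands: loss of mild myalgia is a possibility that turns on forms not included in the documents.

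The reply adds that the primary safety comparison is a composite, that individual events are only described, that no equivalence or non-inferiority test could be tipped, and that every rate above is assumed. All of this is correct and limits the consequence.

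A reader might go further and infer that the reaction most linked to the high dose is under-counted, so that the arms are made to look alike. The documents do not support that. The adult transplant trial in B.4.a, the closest population, noted no difference in systemic reactions. Fatigue is also named for the high dose in B.4.b and B.4.e. Unequal loss could widen the difference as well as narrow it.

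Finally, version 6.0 is dated August 2019, after the two seasons that enrolled new subjects (C.4), so a new table wording would reach only repeaters. This also stands, and it makes the scoring rule the main remedy.

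None of these points gives myalgia with unchanged activity a grade.

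**Conclusion.** The grading defect is established from the text alone. Table 5 leaves a named solicited symptom without a grade at its mildest, so myalgia severity cannot be read alongside fatigue, headache or nausea.

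The effect on frequency is conditional. It requires that the memory aid or case report form counts only graded symptoms. The absolute difference in myalgia is then understated by the factor (1 − *m*) if the loss is similar in both arms; on the assumed rates, 15 points becomes 3.8 to 11.3. The identical rows look like a copied entry, but the documents do not show the cause. The point is worth correcting because the remedy is cheap, but it does not threaten the primary immunogenicity result.

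**What to change.** **Main change.** Add one sentence to C.17.c: any body ache/myalgia reported on the memory aid counts as a solicited AE of at least Grade 1, whatever the activity level, in all seasons. Settle it before the arms are compared unblinded, and summarize general activity level as its own item.

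**Secondary change.** For any remaining vaccinations, bring the myalgia row of Table 5 and the memory aid into line with the fatigue, headache and nausea rows. If the wording changes, report myalgia severity by scale version and do not pool it silently across seasons.

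**Cost.** One sentence, one table row and a form revision. Recorded myalgia rates may rise in both arms, and two scale versions may exist across seasons. If earlier memory aids carried only the graded wording, mild cases from those seasons cannot be recovered, and the report should state this as a limitation.

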## 7. Reporting Adverse Events:

The investigator is responsible for reporting:

- Any Grade 3 Adverse event that is not attributable to underlying disease for which the transplant was undertaken, **or** not attributable to GVHD, **or** not attributable to complications of immunosuppressive medications that are observed or reported through 7 days following vaccination (Day 0 through Day 7), regardless of their relationship to study product.
- Any other AE will not be reported unless it meets the SAE criteria (see Section 16.f).

Initial vaccine reactions will be assessed for at least 15 minutes after each vaccination. Subjects will be asked to record both solicited vaccine reactions and any unsolicited AEs on a memory aid for 7+ days after each vaccination (Day 0 through Day 7). Study personnel will attempt to contact the subjects by telephone and/or electronic communication at 1-3 days and 8-10 days after vaccination to review any AEs and SAEs. Adverse events and SAEs will be collected through 7 days following vaccination.

**Solicited systemic AEs** will be collected for 7+ days post each vaccination and will include the following: fevers, headache, fatigue/malaise, nausea, body ache/myalgia, general activity level, and vomiting. **Solicited injection site AEs** will include the following: pain, tenderness, redness/erythema, and swelling/induration at injection site.

**Reporting of Deviations:** All deviations will be reported to the Institutional Review Board (IRB) at the time of annual continuing review. Note: if the deviation affects patient safety and/or risk, the event will be reported immediately.

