#### **Visit 1: Day 0:**

- Subject will sign written Informed Consent if not already signed prior to Visit 1.
- Brief review of Medical history
  - Inclusion/exclusion criteria will be checked.
  - Prior/concomitant medications will be recorded.
  - Written documentation of prior influenza immunizations post-transplant will be collected.
- Targeted physical examination will be conducted including measurement of oral temperature (must be  $\leq 100.4^{\circ}\text{F}/38^{\circ}\text{C}$ ). Except for oral temperature, if a physical exam is completed as a part of standard of care, another physical exam does not need to be completed.
- For females of childbearing potential a pregnancy test will be performed.

- Approximately 30-60 mL of blood will be collected by venipuncture or from a central line prior to vaccination for HAI and MN assays to influenza virus antigens, phenotypic B, and T cell responses, B and T cell specific influenza responses, CBC d/p, quantitative CD4+/CD8+/CD19+ levels, and quantitative serum IgG and IgM concentrations (if CBC d/p, quantitative CD4+, CD8+, CD19+, IgM, and IgG are obtained as part of standard of care prior to enrollment and on the same calendar day as vaccination, these data will be collected and will not need to be repeated).
- Study vaccine will be administered.
- Study staff will observe the subjects closely for at least 15 minutes post-vaccination, with appropriate medical treatment readily available in case of rare anaphylactic reaction following the administration of vaccines.
- If IVIG/SCIG is given the same day, it must be given after the vaccination, and a second blood draw will be obtained post-IVIG/SCIG if administered on same calendar day.
- A memory aid form with reaction measurements, a measurement gauge, thermometer and instructions will be provided for the subject to record oral temperatures and any general or local reactions occurring during the vaccination day (day 0) and the next 7 days. Information on the memory aid form will be collected from the subject through telephone calls and/or electronic communication in the week following vaccination or received by mail. . If memory aid data were not received by any of the methods mentioned, subjects may return it on the day of their next visit.

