- The subject will be given contact information for study personnel. The subject will be educated about any potential reactions following vaccination. They will be instructed to contact study personnel for reactions that are Grade 3, as well as any other medical event that is concerning to subject.
- A nasal swab for PCR testing for influenza and other respiratory viruses will be obtained regardless of symptoms.

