## Methods and Timing for Assessing, Recording, and Analyzing Safety Parameters

### a. Adverse Events, Reactogenicity, Serious Adverse Events:

The investigator is responsible for reporting:

- Any Grade 3 Adverse Event that is not attributable to underlying disease for which the transplant was undertaken, **or** not attributable to GVHD, **or** not attributable to complications of immunosuppressive medications **and** are observed or reported through 7 days following vaccination, regardless of their relationship to study product.
- Any other AE will not be reported unless it meets the SAE criteria (see Section 16.f).

A physician, nurse, NP, and/or physician's assistant will assess initial vaccine reactions for at least 15 minutes after vaccination. Subjects will be asked to record both solicited vaccine reactions (reactogenicity) and any unsolicited AEs on a memory aid for 7+ days after each vaccination (Day 0 through Day 7). Study personnel will attempt to contact the subjects by telephone and/or electronic communication at 1 to 3 days and again 8-10 days after each vaccination to review any AEs and SAEs.

Adverse events and SAEs will be collected through 7 days following each vaccination. Adverse events will be followed until resolution or until considered stable. **Solicited injection site AEs** will include the following: pain, tenderness, erythema/redness, and swelling/induration (**Table 4**). **Solicited systemic AEs** will be

collected for 7+ days post each vaccination and will include the following: fevers, fatigue/malaise, headache, nausea, body ache/myalgia, generally activity, and vomiting (**Table 5**).

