**g. Reporting Procedures:**

Adverse events including local and systemic reactions not meeting the criteria for SAEs will be captured on the appropriate case report form (CRF). Information to be collected for unsolicited adverse events includes event description, date of onset, investigator assessment of severity, investigator assessment of relationship to study product, date of resolution of the event, seriousness, and outcome. The severity of non-serious AEs will be assessed by a licensed clinician (i.e., medical doctor, nurse, nurse practitioner, physician's assistant). The relationship of non-serious AEs will be assessed by a licensed clinician (i.e., medical doctor, nurse practitioner, physician assistant) listed on the Form FDA 1572. AEs occurring during the AE reporting period of the study will be documented appropriately regardless of relationship. AEs will be followed to adequate resolution or until considered stable.

Any medical condition that is present at screening will be considered a baseline condition and will not be reported as an AE. If the severity of any pre-existing medical condition increases during the study period, then it will be recorded as an AE.

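### Table 5 pairs Celsius and Fahrenheit fever limits that are not the same temperature, so the grade of a fever near 39 °C (and at 38.3 °C) depends on the unit used

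*Combined protocol and SAP*

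**What the plan says.** The fever row of Table 5 (section C.16.e, Reactogenicity) gives every limit in both units. Grade 1 is "≥38.0 - <38.3 ≥100.4 < 101° F" and Grade 2 is "≥38.3 - <39 ≥ 101 - < 102° F". Grade 3 is 39 °C or above, printed with 102 °F or above. The row is labelled oral temperature in °C.

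Grade 3 status is used in three places:

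- **Reporting.** Section C.7 requires the investigator to report "Any Grade 3 Adverse event that is not attributable to underlying disease for which the transplant was undertaken", with like exclusions for GVHD and complications of immunosuppression, through Day 7. Sections C.7 and C.16.a then add: "Any other AE will not be reported unless it meets the SAE criteria".
- **Subject instruction.** Under Visit 1 in section C.14, subjects are educated about reactions and "They will be instructed to contact study personnel for reactions that are Grade 3". Visit 2 repeats this.
- **Analysis.** Section C.17.c summarises severity descriptively by group and type of event. Severity of solicited systemic events, fever included, is secondary objective iii.

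Temperatures come from the subject's own readings. At Visit 1 a memory aid, a gauge, "thermometer and instructions will be provided for the subject to record oral temperatures". No unit is stated there.

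**The concern.** A grading table printed in two units should give one grade per temperature. If the paired limits differ, there is a band in which the grade depends on the column the grader reads. At the Grade 2/3 limit that band straddles the only severity line with a reporting consequence. A non-serious fever on the Grade 2 side falls outside investigator reporting. On the Grade 3 side it is reportable, unless one of the attribution exclusions applies. The same limit decides whether the call instruction is triggered by grade, and in which severity category the fever is tabulated.

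**Working it through.** **Inputs.** All limits come from the fever row of Table 5: Grade 1 from 38.0 °C / 100.4 °F, Grade 2 from 38.3 °C / 101 °F, Grade 3 from 39 °C / 102 °F.

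**Formulas.** C = (F − 32) × 5/9 and F = C × 9/5 + 32.

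**Step 1: convert each printed pair.**

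| Limit | Celsius limit in °F | Fahrenheit limit in °C | Gap |
|---|---|---|---|
| Start of Grade 1 | 38.0 × 1.8 + 32 = 100.4 | (100.4 − 32) × 5/9 = 38.0 | none |
| Grade 1/2 | 38.3 × 1.8 + 32 = 100.94 | (101 − 32) × 5/9 = 38.33 | 0.06 °F (0.03 °C) |
| Grade 2/3 | 39 × 1.8 + 32 = 102.2 | (102 − 32) × 5/9 = 38.89 | 0.2 °F (0.11 °C) |

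Only the first pair is reproduced. At Grade 2/3 the Fahrenheit limit is the lower temperature. At Grade 1/2 the Celsius limit is the lower one, so the two mismatches run in opposite directions.

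**Step 2: grade every tenth-degree reading on both scales.** These are the readings that disagree:

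| Reading | Equivalent | Grade by °C limit | Grade by °F limit |
|---|---|---|---|
| 38.3 °C | 100.94 °F | 2 | 1 |
| 38.9 °C | 102.02 °F | 2 | 3 |
| 102.0 °F | 38.89 °C | 2 | 3 |
| 102.1 °F | 38.94 °C | 2 | 3 |

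On a thermometer reading in 0.1 °F, the Celsius limits assign Grade 2 to 101.0 through 102.1 °F, which is 12 readings; 2 of them change grade. On one reading in 0.1 °C, Grade 2 is 38.3 through 38.9 °C, which is 7 readings; 2 of them change, one up and one down. These are shares of the scale, not of subjects.

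**Step 3: does rounding explain it?** The 39 °C / 102 °F pair agrees only if conversions are rounded to whole degrees, yet the same row uses tenths (38.3 and 100.4). Rounding during conversion can also create a discrepancy: 100.9 °F is 38.28 °C, Grade 1 on both scales, but becomes Grade 2 if first rounded to 38.3 °C.

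**Step 4: could this be a fault in reading the table?** Unlikely. Within each unit the top of Grade 2 meets the bottom of Grade 3 (39 with 39, 102 with 102), so the row is internally complete.

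**The case against.** The best defence is that Celsius governs. The row carries a °C label, Fahrenheit is printed second, and the influenza-like-illness fever criterion in sections C.1 and C.14 also gives Celsius first with a whole-degree Fahrenheit figure. On that reading 102 °F is a rounded gloss. This has some force, but a label is not a precedence rule. The criterion for delaying vaccination in section C.4 and the Visit 1 temperature check put Fahrenheit first, and nothing tells a grader to ignore the Fahrenheit limits.

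Other parts of the defence stand and limit the point:

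- **Mixed thermometers are not shown.** A reader might infer that sites or homes used different units. The study supplies the thermometer, and no section says units vary. The protocol simply leaves the unit unstated.
- **The main safety result is not at risk.** The primary safety estimate in section C.17.c counts subjects with any solicited event. The lowest fever limit converts exactly, so whether a fever counts at all does not depend on unit.
- **Halting is not at risk.** Halting rule 2 in section C.16.j, which counts Grade 3 reactogenicity events, leaves out Grade 3 fever.
- **Fever data are not lost.** Section C.16.g has non-serious reactions entered on the case report form.
- **Contact does not hang on grade alone.** Subjects are also told to call about any medical event that worries them.
- **No formal severity comparison is affected.** Section C.17.c describes severity and does not test it.

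**Conclusion.** The fever row is wrong as written, at two limits, and the effect is small. A temperature from 38.89 °C to below 39.0 °C (102.0 to below 102.2 °F) is Grade 2 or Grade 3 according to the unit. It can therefore cross or miss the Grade 3 reporting line (subject to the attribution exclusions), the grade-based call instruction and the Grade 3 category of the severity summary. The Grade 1/2 mismatch affects only the severity summary.

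The conversions need no assumption. The practical effect assumes that graders could use either printed limit, which the protocol permits because it names no governing unit. It is tempting to go further and estimate how many of the 138 subjects are affected, or to say that one reclassified case would be a large share of the Grade 3 fevers. The documents give no fever rate, so neither statement can be supported. Nor is there reason to expect bias between groups: allocation is balanced within site and study staff are blinded (sections C.5.a and C.16.m), so nothing ties the unit to the vaccine.

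**What to change.** 1. Reconcile the Celsius and Fahrenheit limits in the fever row of Table 5, or state that one unit governs. The sponsor decides which limit to keep. The Grade 2/3 limit appears in both the Grade 2 and Grade 3 cells, and the Grade 1/2 limit in both the Grade 1 and Grade 2 cells, so all affected cells must change together.
2. State the memory-aid unit, and store each temperature as recorded, with its unit.
3. Derive the fever grade by program from one scale for all subjects and seasons, converting without intermediate rounding.
4. Re-grade readings already recorded by the same rule, and check whether any Grade 3 report or severity count changes.

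The cost is one table row, one derivation rule and one re-run. No new data are needed where the recorded value was kept: fever readings near 38 to 39 in Celsius and 100 to 102 in Fahrenheit cannot be confused, so a missing unit can be recovered unless the value was converted before entry.
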